Study Design: In this safety study of nivolumab monotherapy, subjects will undergo screening evaluations to determine eligibility within 28 days prior to first dose. Eligible subjects will be treated with nivolumab administered intravenously over 30 minutes at 3 mg/kg every two weeks. Each 14 day dosing period will constitute a cycle. After 1 year (52 weeks) of treatment all subjects who are still on treatment will be randomized (1:1) to one of the two cohorts, Cohort A or Cohort B.

- Cohort A: Subjects randomized to Cohort A will continue to receive treatment until disease progression, unacceptable toxicity, or withdrawal of informed consent.
- Cohort B: Subjects randomized to Cohort B will discontinue treatment at 1 year (52 weeks). After randomization, subjects will remain on the study and will follow all study assessments [REDACTED] Upon progression, subjects can receive retreatment. If subjects are [REDACTED]

[REDACTED] Subjects who are retreated can continue to receive study drug until further progression, unacceptable toxicity, or withdrawal of informed consent.

Study treatment can continue beyond initial investigator assessed progression, as specified in criteria presented in [Section 4.3.4 Treatment Beyond Disease Progression](#).

The study will enroll subjects into 4 subgroups as detailed in [Table 3.1-1](#). Enrollment will open first to subgroup 1 only. A decision to open enrollment for each of the other subgroups 2-4 will be dependent upon the sponsor review of data from the ongoing Phase 2 and 3 studies for each patient population. The decision will take into account the overall risk/benefit profile for each patient population and the determination will be made whether or not to collect additional safety and efficacy data to supplement that already collected.

At the time of Protocol Amendment 01 (June 2014), all subgroups were opened.

Protocol Amendment 03 (November 2014) allowed for continued enrollment beyond 780 subjects in two of the study subgroups. However, as of Protocol Amendment 04 (December 2014), enrollment under Amendment 03 will stop, but enrollment will continue until 500 additional subjects are treated. Enrollment will continue until a total of 1280 subjects are treated.

[REDACTED]

Under Protocol Amendment 04, all subjects will receive nivolumab by IV infusion administered over 30 minutes, including new and existing subjects enrolled in the study and subjects enrolled under Amendment 02.

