Any Skin AEs	3 (18)	0	5 (28)	0	27 (31)	0	12 (22)	0	28 (21)	1 (1)	75 (25)	1 (0.3)
Rash	3 (18)	0	3 (17)	0	20 (23)	0	5 (9)	0	14 (11)	0	45 (15)	0
Pruritus	0	0	1 (6)	0	15 (17)	0	3 (6)	0	13 (10)	1 (1)	32 (11)	1 (0.3)
Any GI AE	1 (6)	0	2 (11)	0	19 (22)	0	7 (13)	0	14 (11)	3 (2)	43 (14)	3 (1)
Diarrhea	1 (6)	0	2 (11)	0	19 (22)	0	6 (11)	0	13 (10)	3 (2)	41 (13)	3 (1)
Any hepatic AE	0	0	2 (11)	0	8 (9)	0	3 (6)	2 (4)	5 (4)	2 (2)	18 (6)	4 (1)
ALT increased	0	0	1 (6)	0	6 (7)	0	1 (2)	0	3 (2)	1 (1)	11 (4)	1 (0.3)
Any Pulmonary AE	1 (6)	0	1 (6)	0	6 (7)	3 (4)	2 (4)	0	7 (5)	3 (2)	17 (6)	6 (2)
Pneumonitis	1 (6)	0	0	0	4 (5)	2 (2)	1 (2)	0	6 (5)	2 (2)	12 (4)	4 (1)
Infusion reaction	0	0	1 (6)	0	3 (4)	0	3 (6)	0	8 (6)	2 (2)	15 (5)	2 (1)
Infusion-related reaction	0	0	1 (6)	0	3 (4)	0	3 (6)	0	5 (4)	0	12 (4)	0
Hypersensitivity	0	0	0	0	0	0	1 (1.9)	0	3 (2)	2 (2)	4 (1)	2 (1)

Abbreviations: ALT: alanine aminotransferase, TSH: thyroid stimulating hormone

Source: Preliminary data, MDX1106-03. Clinical data cut-off date: 18-Mar-2013

1.1.1 *Rationale for Study Design*

The main objective of the study is to provide additional insight into the frequency of high-grade select AEs and their outcome, and thus supplement the growing safety database of nivolumab-treated subjects. This study will treat approximately 780 subjects in order to estimate the incidence of the rare high grade (CTCAE V4 Grade 3-4 and Grade 5) treatment-related select AEs with greater precision and characterize their outcome (between 0 and 2% incidence per event type in NSCLC subjects treated with nivolumab monotherapy in previous studies).

The safety assessment for the patient subgroups 1-3 is expected to be similar and hence the size of those individual cohorts will not be fixed. There is the possibility that the safety assessment of subgroup 4 (PS2) could be different and so enrollment is limited to 100 subjects.

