Also, the large number of subjects enrolled will allow an opportunity to describe, as an exploratory objective, two different treatment durations in terms of safety, efficacy, and patient-reported outcomes (PRO) data. In study MDX1106-03, after 48 weeks of treatment with nivolumab at the 3 mg/kg dose level, 27% of the NSCLC subjects were still on treatment (95% CI: 12.7%, 41.3%). Following on that observation, in the current study, subjects who are still benefiting from the drug after completing 1 year of treatment will be randomized 1:1 in two cohorts. Subjects randomized to Cohort A will continue on treatment until progression, unacceptable toxicity, or withdrawal of informed consent. Subjects randomized to Cohort B will remain on study but will discontinue treatment. Upon disease progression, subjects in Cohort B will be allowed to resume treatment. Subjects randomized to Cohort B who restart treatment will then continue on treatment until progression, unacceptable toxicity, or withdrawal of informed consent.

An additional 500 subjects will be treated under Protocol Amendment 04 (December 2014) to continue collecting safety information and to characterize the outcome of immune-mediated side effects. These additional data will provide a larger data set to inform the risk/benefit profile of the use of nivolumab in lung cancer patients and will help to further clarify the effectiveness of the current treatment algorithms for managing drug- mediated toxicities (See [Appendix 2](#) for Management Algorithms).

1.1.2 *Rationale for Subject Subgroups*

Obtaining additional data on the incidence and outcome of high grade (Grade 3-4 and Grade 5) select events in a similar patient population as that included in the nivolumab registrational NSCLC studies is warranted to further support the assessment of risk/benefit.

Obtaining similar data in patient populations that have been previously excluded from the registrational studies (ie. subjects with PS 2) will provide critical information for the nivolumab clinical development program, and also for medical oncologists when making treatment decisions. Treatment with nivolumab in subjects with PS 2 is planned to allow for signal detection for both safety and efficacy as an exploratory objective (subgroup 4). This data will inform if further investigation of the risk/benefit profile of nivolumab in this subject subset is justified.

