- admission encountered for another life circumstance that carries no bearing on health status and requires no medical/surgical intervention (eg, lack of housing, economic inadequacy, caregiver respite, family circumstances, administrative reason).

6.1.1 *Serious Adverse Event Collection and Reporting*

Following the subject's written consent to participate in the study, all SAEs, whether related or not related to study drug, must be collected, including those thought to be associated with protocol-specified procedures. All SAEs must be collected that occur during the screening period and within 100 days of discontinuation of dosing. If applicable, SAEs must be collected that relate to any later protocol-specified procedure (eg, a follow-up skin biopsy).

The investigator should report any SAE that occurs after these time periods and that is believed to be related to study drug or protocol-specified procedure.

An SAE report should be completed for any event where doubt exists regarding its seriousness.

If the investigator believes that an SAE is not related to study drug, but is potentially related to the conditions of the study (such as withdrawal of previous therapy or a complication of a study procedure), the relationship should be specified in the narrative section of the SAE Report Form.

SAEs, whether related or not related to study drug, and pregnancies must be reported to BMS (or designee) within 24 hours. SAEs must be recorded on the SAE Report Form; pregnancies on a Pregnancy Surveillance Form (electronic or paper forms). When using paper forms, the reports are to be transmitted via email or confirmed facsimile (fax) transmission to:

SAE Email Address: Refer to Contact Information list.

SAE Facsimile Number: Refer to Contact Information list.

For studies capturing SAEs through electronic data capture (EDC), electronic submission is the required method for reporting. The paper forms should be used and submitted immediately, only

in the event the electronic system is unavailable for transmission. When paper forms are used, the original paper forms are to remain on site.

SAE Telephone Contact (required for SAE and pregnancy reporting): Refer to Contact Information list.

If only limited information is initially available, follow-up reports are required. (Note: Follow-up SAE reports should include the same investigator term(s) initially reported.)

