6.2.1 Nonserious Adverse Event Collection and Reporting

The collection of nonserious AE information should begin at initiation of study drug. Nonserious AE information should also be collected from the start of a placebo lead-in period or other observational period intended to establish a baseline status for the subjects.

Nonserious AEs should be followed to resolution or stabilization, or reported as SAEs if they become serious (see [Section 6.1.1](#)). Follow-up is also required for nonserious AEs that cause interruption or discontinuation of study drug and for those present at the end of study treatment as appropriate. All identified nonserious AEs must be recorded and described on the nonserious AE page of the CRF (paper or electronic).

Completion of supplemental CRFs may be requested for AEs and/or laboratory abnormalities that are reported/identified during the course of the study.

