8.4.2 Primary Analyses

The number and percentage of subjects who report high grade (Grade 3-4 and Grade 5) treatment related select adverse events will be summarized for all treated subjects. High grade (Grade 3-4 and Grade 5) treatment related select adverse events will be tabulated using worst grade per NCI CTCAE v4.0 criteria by system organ class and Medical Dictionary for Regulatory Affairs (MedDRA) preferred term.

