Descriptive statistics of safety (AE and lab data) including incidence, median values using the Kaplan-Meier (KM) product-limit method with 95% CI using Brookmeyer and Crowley method of time to onset and time to resolution, and rate of discontinuation due to event occurrence will be presented for all treated subjects, by tumor histology (SQ or NSQ), by subject subgroups, and all randomized subjects for Cohorts A and B. Time to onset is calculated from first dosing date to the event onset date. If a subject never experienced the given AE, the subject will be censored at the last contact date. Time to resolution is calculated from the AE onset date to AE end date. If an AE is ongoing at the time of analysis, the time to resolution will be censored at the last contact date.

8.4.4.2 *Efficacy Analyses*

[figure not shown]
OS and PFS will be summarized by KM product-limit method for all treated subjects and all response evaluable subjects, respectively. Median values of OS and PFS, along with two-sided 95% CI using Brookmeyer and Crowley method, will be calculated. Survival rates at 6, 12, 18 and 24 months will also be estimated using KM estimates on the OS curve for all treated subjects. Associated two-sided 95% CIs will be calculated using the Greenwood formula. This analysis will be performed for all treated subjects or for all response evaluable subjects for PFS. This analysis will also be performed by tumor histology (SQ or NSQ), by subject subgroups, and all randomized subjects for Cohorts A and B.

The ORR will be summarized by binomial response rates and their corresponding two-sided 95% exact CIs using the Clopper-Pearson method. This analysis will be performed for all response evaluable subjects. This analysis will also be performed by tumor histology (SQ or NSQ), by subject subgroups, and all randomized subjects for Cohorts A and B.

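### Select-AE incidence by subgroup is planned only as a crude percentage, so it moves with time on drug and could hide a moderately higher hazard in PS 2

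*Combined protocol and SAP*

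**What the plan says.** The primary analysis (section 8.4.2) reports "The number and percentage of subjects who report high grade (Grade 3-4 and Grade 5) treatment related select adverse events" among all treated subjects. Section 8.4.3 does the same for select events of any cause. Section 8.4.4.1 repeats incidence by histology, subject subgroup and Cohorts A and B: "Descriptive statistics of safety (AE and lab data) including incidence, median values using the Kaplan-Meier (KM) product-limit method". Time to onset runs from first dose, and event-free subjects are censored at last contact (8.4.3, 8.4.4.1). Table 5.1-3 continues survival contact every 3 months for up to 5 years from the start of therapy.

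On collection, section 6.1.1 says: "All SAEs must be collected that occur during the screening period and within 100 days of discontinuation of dosing". It then adds: "The investigator should report any SAE that occurs after these time periods and that is believed to be related to study drug". For other events, section 6.2.1 gives a start, "The collection of nonserious AE information should begin at initiation of study drug", but no end. Table 5.1-3 limits AE follow-up after 100 days to drug-related events that are still ongoing.

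On PS 2, section 1.1.1 says: "There is the possibility that the safety assessment of subgroup 4 (PS2) could be different", and caps the subgroup at 100. Section 1.1.2 makes safety and efficacy signal detection in these subjects an exploratory aim that will inform whether further study is justified.

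**The concern.** A crude percentage compares groups fairly only if they are watched for similar lengths of time. Here the period of full collection is time on drug plus 100 days, cut short by death. PS 2 subjects could plausibly stop or die sooner than PS 0-1 subjects. If they do, their percentage falls for a reason unrelated to the risk per week of treatment. A reassuring PS 2 percentage could then be read as no signal when the hazard is in fact higher. The same applies, less sharply, to any contrast between subgroups 1-3 or between SQ and NSQ if time on drug differs.

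The planned time-to-onset summary does not correct this. A Kaplan-Meier median needs half of the subjects to have the event, and at about 5% it will in practice not be reached. Censoring at last contact also counts months of survival calls, after active AE collection has ended, as event-free time.

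**Working it through.** **The plan's own figures.** Exact (Clopper-Pearson) limits reproduce all 16 rows of Table 8.1-1: 39/780 gives 3.58-6.77% and 5/100 gives 1.64-11.28%. That arithmetic is correct and is not in question.

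**Inputs from the documents.**
- Reference incidence 5%: Grade 3-4 treatment-related select AEs in 129 NSCLC subjects (1.1).
- Time on drug: 10/37 (27%) still on treatment at week 48 (1.1.1, Synopsis). Section 8.1.1 describes the same fraction as progression-free.
- Window after the last dose: W = 100/7 = 14.29 weeks.

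**Assumptions.** Time on drug is exponential. PS 2 median time on drug is 4 to 20 weeks, a range chosen because the documents give none.

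**Model.** The stopping rate is μ = −ln(10/37)/48 = 0.02726 per week, so the reference mean is 36.7 weeks and the median 25.4. With constant event hazard λ:

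crude incidence = 1 − [μ/(μ+λ)]·exp(−λW)

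Setting this to 5% in the reference group gives λ = 0.00102 per week. Check: 1 − (0.02726/0.02828)(0.9855) = 0.050. For a PS 2 median of 8 weeks (μ = 0.0866) and hazard ratio 1.5 (λ = 0.00153): 1 − (0.08664/0.08817)(0.9784) = 3.9%.

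The break-even hazard ratio, below which PS 2 still shows the lower percentage, is close to the ratio of mean windows. At 8 weeks that is (36.7 + 14.3)/(11.5 + 14.3) = 1.97.

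| PS 2 median weeks (assumed) | Crude %, equal hazard | Crude %, HR 1.5 | Break-even HR, constant hazard | with early death* | hazard ×0.25 after week 12 |
|---|---|---|---|---|---|
| 4 | 2.0 | 3.0 | 2.51 | 3.45 | 1.54 |
| 8 | 2.6 | 3.9 | 1.96 | 2.45 | 1.40 |
| 12 | 3.2 | 4.7 | 1.60 | 1.90 | 1.28 |
| 16 | 3.7 | 5.5 | 1.36 | 1.55 | 1.18 |
| 20 | 4.3 | 6.3 | 1.18 | 1.31 | 1.10 |

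*Assumed median survival after stopping: 26 weeks for the reference, 8 weeks for PS 2.

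If all hazard lies in the first 12 weeks and the full 100 days are observed, break-even is 1.0 and there is no reversal. At a 2% reference incidence the break-even values are almost unchanged.

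**Would the added measures help?** I simulated 3 million subjects per group with a PS 2 median of 8 weeks, a true hazard ratio of 1.5, early death as above, and λ = 0.00107 (recalibrated to 5%):

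| Measure | Reference | PS 2 |
|---|---|---|
| Crude % | 5.0 | 3.1 |
| First events per 100 person-years at risk | 5.6 | 8.4 |
| Cumulative incidence at 12 weeks, death competing | 1.3% | 1.7% |
| Cumulative incidence at 24 weeks, death competing | 2.4% | 2.7% |

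The crude order is wrong and the other three are right, although the 24-week gap is narrow because early deaths remove PS 2 subjects from risk.

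Censoring was tested in a separate run at a slightly lower base hazard (reference crude 4.9%). Kaplan-Meier at 26 weeks gave 2.7% v 4.0% when censored at the end of AE collection, and 2.6% v 3.7% when censored at last contact.

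**Precision.** With 100 PS 2 subjects and a mean window of about 21 weeks (12 weeks on drug, early death), person-time is 100 × 21/52.18 ≈ 40 years. Expected events at 8.4 per 100 are about 3.4. Three events give an exact Poisson 95% CI of 0.619/40 to 8.767/40, or about 1.5 to 22 per 100 person-years.

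**The case against.** Late events are not simply lost. Related SAEs after 100 days must still be reported, which covers much of a Grade 3-5 treatment-related endpoint. Nonserious events have no stated end date, and section 3.6 can be read as following select AEs beyond 100 days. This stands against any claim that collection stops at 100 days, and the hard cut-off in the model is a simplification. But late reporting rests on the investigator's causality judgement, is less active than scheduled visits, and leaves out unrelated late SAEs, which belong to the any-cause secondary endpoint.

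The PS 2 reversal rests on assumed exposure and hazard shape. That also stands: it is a possibility, not a demonstrated bias. Nor does the plan base a formal decision on this contrast, since the PS 2 aim is exploratory.

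A reader might infer that person-time rates would reveal the signal. With a CI of about 1.5 to 22 per 100 around three events, they could not establish it. They would remove a directional distortion, not the imprecision.

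A reader might also infer that the primary percentage needs repair because "Subjects randomized to Cohort B will discontinue treatment at 1 year (52 weeks". The documents do not support that. The objective is incidence in treated subjects, incidence by Cohort A and B is already planned (8.4.4.1), and Cohort B stays on the on-study visit schedule (3.5). In the model above, stopping half of those still on drug at week 52 moves 5.0% only to about 4.6%, inside the planned interval of 3.58-6.77%.

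**Conclusion.** The point holds for the subgroup and histology summaries. Incidence there is a crude percentage whose value depends on time on drug, and the planned Kaplan-Meier medians do not correct it. If PS 2 subjects have short exposure, a hazard up to about 1.1 to 2.5 times higher could show as an equal or lower percentage, and up to about 3.5 times with early death. Those figures assume exponential time on drug, a PS 2 median of 4 to 20 weeks, a full collection window of 100 days after the last dose, and either a constant hazard or one falling to a quarter after week 12. With all risk in the first 12 weeks and full observation, the effect disappears. The crude percentage remains a valid answer to how many treated subjects had an event, and it should stay as the primary estimate.

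**What to change.** Leave 8.4.2 as it is. In 8.4.3 and 8.4.4.1 add, for subgroups 1-4 and for SQ and NSQ:

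1. First events per 100 person-years at risk, counting time on drug plus 100 days and ending at death, with exact Poisson 95% CI.
2. Cumulative incidence at fixed times from first dose, such as 12 and 24 weeks, with death as a competing event and 95% CI. Censor at the end of the AE collection window, not at last contact.

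State that window explicitly for serious and nonserious events, and say how off-drug time in Cohort B counts. Label the PS 2 figures as descriptive and always show their CIs.

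The cost is a few table columns from first-dose, last-dose, onset and death dates already collected. The downside is that a single rate assumes a roughly constant hazard. With equal hazards that fall to a quarter after week 12 (0.00245 per week before then, PS 2 median 8 weeks, early death), the same simulation gives rates of 5.6 v 8.4 per 100 person-years, a false PS 2 excess. The 12-week cumulative incidences are 2.85% v 2.59%. The rate should therefore never be read without the fixed-time figures.

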The study will close after the last enrolled subject completes 5 year follow up. The duration of the study will be 6.5 years.

Study Population: Patients with Stage 3b/4 NSCLC (squamous or non-squamous histology) who have experienced disease progression or recurrence during or after at least one systemic therapy for advanced or metastatic disease. Subjects must meet all eligibility criteria specified in [Section 3.3](#) of the protocol.

Study Assessments: Main assessments include: Incidence, severity and outcome of select adverse events, and specific related laboratory abnormalities. Exploratory assessments include incidence and severity of all adverse events, laboratory abnormalities, efficacy measures, patient reported outcomes [REDACTED].

Statistical Considerations:

Sample Size: In order to further characterize the frequency and outcome of the rather infrequent treatment related select adverse of high grade (Grade 3-5), the current study will treat approximately 780 subjects with nivolumab. This sample size will allow for estimating an incidence rate of 0.5% (n=4 subjects with events) with a 95% CI (confidence interval) of (0.14%, 1.31%), or an incidence rate of 2% (n=16 subjects with events) with a 95% CI of (1.18%, 3.31%).

This study also includes a randomization step reserved to subjects who received nivolumab for 1 year (52 weeks). In MDX1106-03, 27% of NSCLC subjects (10 of 37) were still on treatment [95% CI of (12.7%, 41.3%)] at Week 48. In the present study any subjects (all subgroups included) who are still benefiting from therapy after 52 weeks (estimated to be between 99 and 322 subjects) will be randomized in order to continue treatment without any change in Cohort A, or to discontinue treatment in Cohort B, respectively.

Endpoints: The primary objective of the study will be assessed by measuring the incidence for high grade (Grade 3-4 and Grade 5) treatment related select adverse events.

The select adverse events of interest are the following: pneumonitis, interstitial nephritis, diarrhea/colitis, hepatitis, rash, endocrinopathies, and hypersensitivity/infusion reaction events.

The secondary objective of the study will be assessed by measuring the following:

- incidence for high grade (Grade 3-4 and Grade 5) select adverse events
- median time to onset, median time to resolution (Grade 3-4) of the select adverse events

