The frequencies of these events in study MDX1106-03 (Phase 1 study; N = 306; heavily pre-treated subjects with different tumor types) are summarized in [Table 1.1-1](#). The treatment-related select AEs of Grade 3-4 observed to date are rather uncommon: 6% overall in study MDX1106-03, while their incidence per category varies between 0.3% and 2% (pulmonary AEs). Of note, the 10 mg/kg cohort had numerically greater frequency of such AEs compared with the other dose levels. In the NSCLC subjects treated in the study (n=129) the overall incidence of Grade 3-4 treatment-related select AEs was 5%: 0% for skin and renal AEs, and endocrinopathies; 1% gastrointestinal, hepatic, and infusion reaction AEs; and 2% for pulmonary events.⁷ Most high-grade events of special interest were observed to have resolved while addressed with systemic corticosteroids and/or other immunosuppressive agents. One exception was Grade 4 pneumonitis considered to have led to death of three subjects: two of them were treated at the 1 mg/kg dose level and had NSCLC and CRC, respectively; the third subject had NSCLC and was treated at the 10 mg/kg dose level.

Specific safety algorithms have been designed for the select categories of AEs, and are implemented in a unified manner in all current studies in the nivolumab program (See [Appendix 2](#) for Management Algorithms). These safety algorithms assist the diagnostic, the assessment of relatedness, and the management of the select AEs, also they are continuously evaluated and adjusted as experience accumulates. The current study will focus on improving precision around the frequency of high-grade select AEs, and on obtaining information on their outcome.

Table 1.1-1: Treatment-related Select Adverse Events by Treatment - All CTC Grades Reported in at Least 10 Treated Subjects in MDX1106-03

Preferred Term	0.1 mg/kg n=17		0.3 mg/kg n=18		1 mg/kg n=86		3 mg/kg n=54		10 mg/kg n=131		Total N=306	
	Any Grade	Grade 3-4	Any Grade	Grade 3-4	Any Grade	Grade 3-4	Any Grade	Grade 3-4	Any Grade	Grade 3-4	Any Grade	Grade 3-4
Any Select AE	8 (47)	1 (5.9)	9 (50)	0	42 (49)	3 (4)	23 (43)	2 (4)	58 (44)	13 (10)	140 (46)	19 (6)
Any Endocrinopathies	4 (24)	0	2 (11)	0	9 (11)	0	4 (7)	0	10 (8)	3 (2)	29 (10)	3 (1)
Endocrinopathies Thyroid	3 (18)	0	2 (11)	0	9 (11)	0	4 (7)	0	8 (6)	2 (2)	26 (9)	2 (1)
Blood TSH increased	2 (12)	0	1 (6)	0	2 (2)	0	2 (4)	0	4 (3)	1 (1)	11 (4)	1 (0.3)
Hypothyroidism	1 (6)	0	1 (6)	0	5 (6)	0	1 (2)	0	3 (2)	1 (1)	11 (4)	1 (0.3)

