1.4.2 Non-small Cell Lung Cancer (NSCLC) - Background and Treatments

Lung cancer is the leading cause of cancer-related deaths globally. An estimated 221,130 new cases of lung cancer will be diagnosed in 2011.⁴⁴ The majority of subjects (approximately 78%) are diagnosed with advanced or metastatic disease. Progression after first-line therapy occurred in nearly all of these subjects and the 5 year survival rate is only 3.6% in the refractory setting.⁴⁴

There is a particular unmet need among patients who have squamous cell NSCLC (representing up to 25% of all NSCLC) as there are few treatment options after first-line therapy (ie, pemetrexed is not a treatment option.^{2,45} In addition, there are targeted therapeutics that are restricted to the non-squamous population due to adverse events (ie, bevacizumab was associated with fatal hemorrhages in squamous cell subjects).⁴⁶ According to NCCN guidelines, the use of single agent chemotherapy is standard-of-care for patients with recurrent and metastatic NSCLC after failure of platinum-based therapy.⁴⁴ Historical median PFS rates in second-line NSCLC are approximately 2.6 - 3.2 months, and median OS rates approximately 6.7 to 8.3 months (longer in the recent ZODIAC trial, 10+ months).^{30,31,45,47,48} Current therapy in second-line includes docetaxel, erlotinib and pemetrexed (only in non-squamous histologies).^{30,31,45} No agent has shown superiority in OS when compared to docetaxel. Different docetaxel schedules (other than the standard q3 weeks), chemotherapy doublets using docetaxel, and other comparative agents have not shown improvement over docetaxel in this line of therapy.^{49,50,51,52,53}

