1.4.3.2 Safety Summary

The overall safety experience with nivolumab, as a monotherapy or in combination with other therapeutics, is based on experience in approximately 1500 subjects treated to date. For monotherapy, the safety profile is similar across tumor types. The one exception is pulmonary inflammation AEs which may be numerically greater in subjects with NSCLC. In some cases it can be difficult to distinguish between nivolumab-related and unrelated causes of pulmonary symptoms and radiographic changes. There was no pattern in the incidence, severity, or causality of AEs to nivolumab dose level.⁹

In MDX1106-03, at the data cut-off date of 18 March 2013, a total of 306 subjects were treated and 303 (99.0%) subjects have at least 1 reported AE regardless of causality. The most frequently reported AEs were fatigue (54.9%), decreased appetite (35.0%), diarrhea (34.3%), nausea (30.1%), and cough (29.4%). Treatment-related AEs were reported in 230 (75.2%) of the 306 subjects. The most frequently reported treatment-related AEs were fatigue (28.1%), rash (14.7%), diarrhea (13.4%), and pruritus (10.5%). Most treatment-related AEs were low grade. Treatment-related high grade (Grade 3-4) AEs were reported in 52 (17.0%) of subjects. The most frequently reported treatment-related high grade AE was fatigue (6.5%). The 10 mg/kg cohort

had numerically greater frequency of high-grade select AEs (events with a potential inflammatory mechanism requiring more frequent monitoring and/or unique intervention such as immunosuppressants and/or endocrine replacement therapy).

Additional details on the safety profile of nivolumab, including results from other clinical studies, are also available in the IB.⁹

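### Kaplan-Meier median time to AE onset censors deaths without the AE, so it is not the time by which half of subjects have had the event

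*Combined protocol and SAP*

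**What the plan says.** Section 8.4.3 (secondary) and Section 8.4.4.1 (exploratory) use the same definition. The clock starts at first dose: "Time to onset is calculated from first dosing date to the event onset date". The rule for everyone else is: "If a subject never experienced the given AE, the subject will be censored at the last contact date". Neither section mentions death, and neither defines last contact.

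Section 8.4.4.1 applies this to all AE and laboratory data: "Descriptive statistics of safety (AE and lab data) including incidence, median values using the Kaplan-Meier (KM) product-limit method with 95% CI". The medians are given for all treated subjects, by histology, by subgroup and for Cohorts A and B. Median time to onset is also a listed secondary endpoint in Section 8.3.2.

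No competing-risk or cumulative-incidence method appears in the document. Survival contact runs every 3 months until death, or to 5 years from the start of therapy (Table 5.1-3, Section 5.4.2). SAE collection runs to 100 days after dosing stops (Section 6.1.1). Beyond that, Table 5.1-3 follows only ongoing drug-related AEs.

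**The concern.** Death without the AE rules the AE out for good. Kaplan-Meier treats that subject as lost from view but still able to have it, with the same future hazard as those who remain. One minus the Kaplan-Meier curve then describes a population in which nobody dies. Its median falls earlier than the time by which half of real subjects are affected, and it can be printed where half never are.

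Death is frequent in this disease. Section 1.4.2 gives historical second-line "median OS rates approximately 6.7 to 8.3 months", and the same sentence notes 10+ months in one trial. In a study whose purpose is safety, a reader will take a median time to onset as guidance on when to expect an event.

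**Working it through.** The plan states no time-to-onset figure to reproduce. The one plan figure used below, for time on treatment, does reproduce. The Synopsis gives "27% of NSCLC subjects (10 of 37) were still on treatment [95% CI of (12.7%, 41.3%)] at Week 48". A Wald interval for 10/37 is 0.270 ± 1.96 × √(0.270 × 0.730/37), which is 12.7% to 41.3%.

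**Inputs**
- Share who ever have the AE, p: 54.9% (fatigue), 35.0% (decreased appetite) and 30.1% (nausea), from Section 1.4.3.2. These are any-cause rates in 306 Phase 1 subjects.
- Median overall survival, M: 6.7, 8.3 and 10 months, from Section 1.4.2. This is an assumed range.
- Assumption: constant hazards, λ for the AE and μ = ln 2/M for death without it.

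**Formulas**
- p = λ/(λ+μ), so λ = μp/(1−p).
- Kaplan-Meier median = ln 2/λ = M(1−p)/p.
- Cumulative incidence with death competing: p(1 − e^(−(λ+μ)t)). At the Kaplan-Meier median this equals p(1 − 2^(−1/p)).
- Competing-risk median = −ln(1 − 0.5/p)/(λ+μ), with λ+μ = μ/(1−p). It exists only if p > 0.5.

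**Worked case** (p = 0.549, M = 6.7): Kaplan-Meier median = 6.7 × 0.451/0.549 = 5.5 months. μ = 0.1035 and λ+μ = 0.1035/0.451 = 0.229. Competing-risk median = 2.416/0.229 = 10.5 months.

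| Ever have AE | KM median, M = 6.7 / 8.3 / 10 | Had AE by then | Competing-risk median |
|---|---|---|---|
| 54.9% | 5.5 / 6.8 / 8.2 months | 39.4% | 10.5 / 13.0 / 15.7 months |
| 35.0% | 12.4 / 15.4 / 18.6 months | 30.2% | none |
| 30.1% | 15.6 / 19.3 / 23.2 months | 27.1% | none |

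**Check with a limited AE window.** A simulation let AEs occur only until 100 days after the last dose and kept subjects at risk until death or 60 months, as the last-contact rule implies. It varied the AE hazard (constant, or halving every 6 or 3 months), M (8.3 or 10 months) and death timing (independent of treatment discontinuation, or only after it). That gives 12 scenarios per AE rate.

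| Ever have AE | Scenarios with a median | KM median (months) | Had AE by then |
|---|---|---|---|
| 54.9% | 12 of 12 | 3.3 to 7.7 | 42% to 48% |
| 45% | 12 of 12 | 6.3 to 12.3 | 38% to 45% |
| 35% | 4 of 12 | 14.9 to 24.0 | 32% to 35% |
| 30% | 2 of 12 | 18.6 and 22.9 | 28% to 29% |

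At 35%, in the eight scenarios without a median, the Kaplan-Meier curve still levels off at 41% to 49%. Moving the censoring date to the end of the AE window does not cure the problem: the 30% and 35% cases then reach a median in 14 of 24 scenarios, instead of 6 of 24.

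**High-grade select AEs.** Section 1.1 puts Grade 3-4 treatment-related select AEs at 5% in NSCLC. The Kaplan-Meier median would be M × 0.95/0.05 = 127 to 190 months. That lies beyond 60 months of follow-up, so it cannot be estimated.

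**The case against.** The strongest defence is that the output is descriptive and untested, and that Section 8.4.4.1 reports crude incidence alongside the median. How many subjects have each AE is therefore answered correctly elsewhere. The plan names medians, not onset curves or Kaplan-Meier percentages. This stands, and it limits the harm. It does not make the printed median right.

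The inputs can also be challenged. The AE rates come from a multi-tumour Phase 1 study at 0.1 to 10 mg/kg, and survival comes from historical second-line NSCLC. Constant hazards give the larger gaps. This stands too: the figures illustrate size and do not forecast it.

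A reader might infer three stronger things that the documents do not support:
- *That every common AE would get a median most subjects never reach.* At 54.9% more than half do have the AE, and the error is a median that is too early. At 45% the shortfall from one half is modest. At 30% and 35% the rule as written gives no median in 18 of 24 scenarios.
- *That subgroup comparisons are distorted by survival differences.* With independent death, the Kaplan-Meier median depends only on the AE hazard. Take the λ that gives 35% at M = 6.7 (0.0557 per month). At M = 10, with μ = 0.0693, the share who ever have the AE becomes 0.0557/0.1250 = 45%, yet the Kaplan-Meier median is 12.4 months in both.
- *That the size is known for laboratory abnormalities.* The same rule applies to them, but the documents give no general rates from which to compute it.

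**Conclusion.** The point holds as a flaw of estimator choice with limited reach. As written, deaths without the AE are censored, and the Kaplan-Meier median of onset does not mean that half of subjects are affected by then.

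For the most common AE the printed median is about half the competing-risk median. That rests on constant hazards and an assumed median survival of 6.7 to 10 months, and the error shrinks if onset is early. For AEs at 30 to 35%, a median with no real counterpart is possible but not the usual result once AE collection is limited. For the high-grade events of the secondary endpoint, the same rule most likely yields no median at all. The primary endpoint and all crude incidences are untouched.

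**What to change.** In Sections 8.4.3 and 8.4.4.1, replace the Kaplan-Meier onset median with the following:
- Aalen-Johansen cumulative incidence at fixed times with 95% CI, treating death without the AE as a competing event.
- An at-risk period that ends when AE collection ends, with that date defined in place of last contact. Cohort B needs its own wording, because Section 3.5 keeps those subjects on the on-study visit schedule after treatment stops. The text should also say whether leaving the collection period alive is censoring or a further competing event.
- Median and range of onset among subjects who had the AE, labelled as conditional on having it.

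The cost is wording, slightly more analysis work with standard software, and no new data. Reported cumulative incidences will be lower than one minus Kaplan-Meier. They will also vary with mortality across subgroups, which the text accompanying the tables should say.
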